EXtended CriteriA treatment for LIver metastases with heavy tumour BURden

Protocol Identification Number: EXCALIBUR

EudraCT Number: 2019-002388-87

PROTOCOL VERSION NO. 25 – 09.02.2021

CONTACT DETAILS

Sponsor: [name] [name], Division Head
Division of Surgery, inflammation and transplantation, Oslo
University Hospital, [name]
[contact]
E-mail: [contact]

Principal Investigator: [name] [name], professor
Dept. of Gastrointestinal surgery, HPB-section,
Oslo University Hospital, [name]
[contact]
E-mail: [contact]

Co-Principal investigator: [name] [name], Senior Consultant in Oncology
Oslo University Hospital, Department of Oncology
[contact]
E-mail: [contact]

Participating Departments:

Department of transplant surgery [name] [name], professor
Oslo University Hospital, Dept.of Transplantation Medicine
[contact]
E-mail: [contact]

Department of oncology: [name] [name], Senior Consultant in Oncology
Oslo University Hospital, Department of Oncology
[contact]
E-mail: [contact]

Department of GI surgery/HPB
section: [name] [name]
Dept. of Gastrointestinal surgery, HPB-section,
Oslo University Hospital, [name]
[contact]
E-mail: [contact]

SIGNATURE PAGE

Title **EX**extended **C**riteri**A** treatment for **L**iver Metastases with heavy tumour **BUR**den

Protocol ID no: **EXCALIBUR**

EudraCT no: 2019-002388-87

I hereby declare that I will conduct the study in compliance with the Protocol, ICH GCP and the applicable regulatory requirements:

Name	Title	Role	Signature	Date
[name] [name]	PI		
[name] [name]	Co-PI		

PROTOCOL SYNOPSIS

Protocol title: **EX**tended **C**riteri**A** treatment for **L**iver **M**etastases with heavy tumour **BUR**den

Sponsor	Oslo university Hospital
Phase and study type	Phase II, Randomized controlled trial
Investigational Medical Product (IMP) (including active comparator and placebo) :	Fluorodeoxyuridine or floxuridine (FUDR, Fresenius Kabi, LLC, USA)
Centers:	Oslo University Hospital
Study Period:	Estimated date of first patient enrolled: February 2021 Anticipated recruitment period: 3 years Estimated date of last patient completed: October 2033
Treatment Duration:	24 weeks (6 cycles of 4 weeks)
Follow-up:	10 years
Objectives	Main study objective: To improve treatment outcome for patients with a heavy burden of colorectal liver metastases and progression on 1 st line chemotherapy. Key secondary objectives: To establish whether the favourable results obtained by use of hepatic artery infusion chemotherapy can be replicated outside of US single centre series.
Endpoints:	Overall Survival (OS) at two years Secondary endpoints: Progression-free survival, overall survival at 5 years, resection/transplantation rate, quality of life.
Study Design:	Three-armed, two-sided, open label, parallel-group, single center, phase II trial.

Main Inclusion Criteria:	
– Multiple colorectal liver metastases (6 or more metastases)– Progression on 1st line chemotherapy
Main Exclusion Criteria	
– Extensive extrahepatic disease
Sample Size:	45 patients
Efficacy Assessments:	Overall survival, progression-free survival and resection rate
Safety Assessments:	Major adverse events/side-effects from chemotherapy and major complications following surgery.
Other Assessments:	Health economy assessment, quality-of-life

TABLE OF CONTENTS

CONTACT DETAILS	2
SIGNATURE PAGE	3
PROTOCOL SYNOPSIS	4
TABLE OF CONTENTS	6
1 INTRODUCTION	9
1.1 Background – Disease.....	9
1.2 Liver resections for Colorectal Liver metastases (CRLM).....	9
1.3 The grey zone.....	10
1.4 Systemic chemotherapy for CRLM.....	10
1.5 Liver transplant for CRLM.....	10
1.6 Hepatic artery infusion (HAI) chemotherapy for CRLM.....	10
1.7 Optimal treatment for patients with CRLM in the grey zone.....	11
1.8 Rationale for the Study and Purpose.....	11
1.9 Research hypothesis.....	11
2 STUDY OBJECTIVES AND RELATED ENDPOINTS	12
3 OVERALL STUDY DESIGN/OVERVIEW OF DESIGN	13
4 STUDY POPULATION	13
4.1 Selection of Study Population.....	13
4.2 Number of Patients.....	14
4.3 Inclusion and exclusion criteria.....	14
4.3.1 Inclusion Excalibur 1	14
4.3.2 Inclusion Excalibur 2	Feil! Bokmerke er ikke definert.
4.4 Exclusion Criteria.....	14
4.4.1 Exclusion.....	Feil! Bokmerke er ikke definert.
5 TREATMENT	15
5.1 Technical procedures.....	15
5.1.1 Second line systemic chemotherapy.....	15
5.1.2 Liver transplantation.....	15
5.1.3 Hepatic Artery infusion (HAI).....	16
5.1.4 Surgical procedure.....	16
5.2 Drug Accountability - IMP.....	20
5.3 Drug Labeling.....	20
5.4 Subject Numbering, different arms of the study.....	21
5.5 Schedule of events.....	21
5.6 By Visit.....	23

List of Abbreviations and Definitions of Terms

Abbreviation or special term	Explanation
AE	Adverse Event
CRF	Case Report Form (electronic/paper)
CSA	Clinical Study Agreement
CTC	Common Toxicity Criteria (for cancer trials only)
CTCAE	Common Terminology Criteria for Adverse Event (for cancer trials only)
DAE	Discontinuation due to Adverse Event
EC	Ethics Committee, synonymous to Institutional Review Board (IRB) and Independent Ethics Committee (IEC)
GCP	Good Clinical Practice
IB	Investigator's Brochure
ICF	Informed Consent Form
ICH	International Conference on Harmonization
IMP	Investigational Medicinal Product (includes active comparator and placebo)
SAE	Serious Adverse Event
SOP	Standard Operating Procedure

1 INTRODUCTION

1.1 Background – Disease

Colorectal cancer (CRC) is the second most frequent malignant disease in Norway (Cancer in Norway 2017). About 50% of the patients will have metastatic disease at time of diagnosis or develop metastatic disease later on. Liver metastases are the most frequent site of metastatic disease. Liver resection is considered the only curative treatment option in CRC patients with liver metastases, however only about 20% of the patients are candidates for liver resection. The treatment option for the majority of the patients is palliative chemotherapy with median overall survival from start of chemotherapy of about 2 years and 10-12 months from starting second line chemotherapy.

1.2 Liver resections for Colorectal Liver metastases (CRLM)

While high-quality data (randomized trials) are lacking, it is generally accepted that the only curative treatment for colorectal liver metastases (CRLM) is surgery. Liver resections are generally well tolerated and safe¹, but some patients recur early and probably have limited or no benefit from surgery. These are hard to identify upfront. Even following three decades of systematic liver surgery for CRLM, there is a lack of robust prognostic scoring systems that have sufficient

discriminatory power to serve as selectors for surgery or non-operative treatment ^{2,3}. Even among patients with very poor prognostic scores, there are some who will survive five years following surgery ⁴, and even without surgery ⁵. Over the decades, the definition of resectability/un-resectability has been steadily modified. Today, any configuration of metastases can be deemed resectable as long as a resection will leave behind a working liver volume of at least 20-30 % of the estimated total liver volume with a functioning arterial inflow, portal venous inflow, draining bile duct and draining hepatic vein.

1.3 The grey zone

As resections are generally well tolerated and adequate prognostication is wanting, there is a tendency to offer resections to patients who have borderline resectable CRLM or who exhibit other non-favourable traits like large or multiple metastases. For patients who have early recurrence of disease, such resections represent a net loss of quality-of-life and an unwanted expenditure for society. Exploring the optimal treatment modality for patients in this grey zone, i.e. with uncertain benefit from surgery, is important to avoid unnecessary resections and providing the optimal treatment for patients in a critical situation.

1.4 Systemic chemotherapy for CRLM

Palliative chemotherapy is in general the only treatment option for the vast majority of non-resectable patients. The expected median overall survival (OS) from start of first line chemotherapy is about 2 years and the 5 years OS is about 10%, although, longer median OS has been obtained in selected patients with good performance status (ECOG 0-1), no (K)RAS or BRAF mutations and left-sided tumors ⁶⁻¹⁰. OS from start of second line chemotherapy is 10-12 months ¹¹.

1.5 Liver transplant for CRLM

Liver transplantation (LTX) has emerged as a possible solution for some patients with unresectable CRLM who otherwise have good prognosis based on available scorings systems ^{12,13}. In patients with non-resectable liver only metastases we have previously shown 5 year OS of 56% compared to 9% in a similar cohort of patients starting first line chemotherapy ⁶, but due to lack of donor organs this will never become the backbone of any treatment modality for a disease as prevalent as CRLM. However, LTX is probably the best treatment option in highly selected patients with non-resectable CRLM liver only disease.

1.6 Hepatic artery infusion (HAI) chemotherapy for CRLM

The biological rationale for intra-arterial chemotherapy is that the hepatic artery rather than the portal vein is responsible for most of the blood supply to liver tumors. Hepatic Artery Infusion (HAI) of a cytotoxic drug floxuridine (FUDR) that has a very high first-pass extraction (ca 95 %) in the liver has shown promising results in selected series for several decades ¹⁴⁻¹⁶. It was developed at Memorial Sloan Kettering Cancer Center (MSKCC, New York, USA) but is currently unavailable in the European Union, because floxuridine is not registered. HAI has however not gained foothold as a standard treatment option for CRLM, and most publications stem from a very few centres. The reasons for this lack of dissemination are unknown but could well be related to the complexity of the treatment algorithm and the lack of modern randomized trials. In Europe several centers in The Netherlands have recently started the HAI treatment procedure as adjuvant treatment in CRC patients who have received liver resection. (Buisman FE et al. *Ann. Surg. Oncol.* 2019 26: 4599-4607. Of the 20 patients included in the study in The Netherlands two patients had Clavien-Dindo complication grade III with reoperation due to replacement of a pump with slow flow-rate and a flipped pump. The treatment administered both at MSKCC and the two centers in The Netherlands consist of 0.12 mg FUDR/kg/day + 35.000 IE heparin + 25 mg dexamethasone in a total volume of 35ml NaCL administered as a continue infusion for 14 days with dose reduction if liver function is affected (Table 2). At day 15 the pump is emptied and refilled with a low dose heparin solution for continuous infusion to avoid coagulation of the catheter. A new cycle is started at day 29. The HAI treatment has been combined with both oxaliplatin and irinotecan regimens combined with 5-FU as systemic chemotherapy ^{14,16,17}. HAI has also been

combined with systemic gemcitabine-oxaliplatin regimen in patients with non-resectable intrahepatic cholangiocarcinoma¹⁸

In the study by D'Angelica in non-resectable CRC patients the response rate was 76%, median overall survival was 38 months and 23 of 49 patients became resectable and received a liver resection. Patients having a liver resection had a 3 year overall survival of 80%. In the study by Pak 33 of 64 non-resectable CRC patients received a liver resection with 5 year overall survival of 36%. These results are better compared to what has been reported by systemic chemotherapy only with median overall survival of about 24 months in most studies. Optimal treatment for patients with CRLM in the grey zone is therefore not yet defined and there is a definite need for further studies.

To optimize treatment for patients with a large tumour burden and borderline resectability, we will compare three treatment modalities in a randomized controlled trial in patients that have progressive disease on 1st line of chemotherapy treatment.

1.7 Rationale for the Study and Purpose

The target population for this study will be patients who based on traditional preoperative criteria have a very dismal prognosis. They will – according to the inclusion criteria – have a large tumour burden and have shown progression on 1st line systemic chemotherapy treatment. Based on previous trials, only 30 % of this patient group will be alive after two years. These patients have today only one treatment modality available: 2nd line systemic chemotherapy. Response can, however, only be expected in a small minority of these patients. As of today, they are not acceptable for inclusion into any of the liver transplant protocols, and hepatic artery infusion (HAI) chemotherapy treatment is not offered in Norway (or any other European country, save the Netherlands, as far as we know).

With such a dismal outcome for these patients, an alternative modality that has the potential to improve survival is highly warranted. While transplantation has such a potential, the access to donor organs will always limit the real-life use of such a treatment and the inclusion of a transplant group in this trial is primarily for proof-of-principle reasons: to benchmark what we have reason to believe is the optimal treatment.

The use of HAI chemotherapy with FUDR has some inherent risks. A laparotomy is necessary to apply the catheter and intra hepatic infusion of FUDR has been reported to cause biliary inflammation and necrosis in a small fraction of the patients. The risk for the latter is however significantly reduced by concomittant steroid infusion. The experiences published from the MSKCC (see further) does however suggest that the drug has few systemic side effects as the first-pass effect in the liver is close to complete, i.e. there is minimal release of active drug into the systemic circulation.

The IMP for use in this protocol does not have a marketing authorization in Europa. The institution that has pioneered the HAI treatment in CRC is Memorial Sloan Kettering Hospital (MSKCC) in New York and the dose is identical to the dose that used in several studies from MSKCC^{14,16} and The Netherlands¹⁷.

1.8 Research hypothesis

In patients with large tumour burden and/or borderline resectability of colorectal liver metastases and progression on 1st line systemic chemotherapy, overall survival following systemic therapy combined with hepatic artery infusion chemotherapy (HAI), or liver transplantation, is better than following conventional systemic chemotherapy alone.

2 STUDY OBJECTIVES AND RELATED ENDPOINTS

The objectives and endpoints of the study are listed in Table 1 below. The primary endpoint is Overall survival at 2 years after randomization. Safety and toxicity grade 3-5 toxicity will be reported.

Table 1 Objectives and related endpoint:

Objectives	Endpoints	Assessment
Primary: Overall survival	Overall survival at 2 years after randomization	Medical records
Secondary: 1. Efficacy	Overall survival (OS), at 5- and 10-years after randomization.	Medical records
Radiological response to treatment	Response rate	CT/MRI-scans RECIST 1.1
2. Efficacy	Resection rate	Medical records
3. Efficacy	Number of patients randomized til HAI receiving HAI-treatment	
4. Efficacy	Quality of life	EORTC QoL C30
Safety all patients	Adverse events in patients receiving chemotherapy	NCI-CTC 5.0 grade III-V toxicity
Safety in patients receiving resection/transplantation.	Major surgical complications	Accordion Grade III - VI
Exploratory	Molecular analyses related to disease-free and overall survival	Biobank stored blood and tumour tissue
	Progression free survival (PFS). (PFS will be calculated both with and without sensing patients receiving resection or transplantation at time of resection/transplantation) Disease free survival after liver resection/transplantation in the different treatment arms	CT/MRI-scans RECIST 1.1

3 OVERALL STUDY DESIGN/OVERVIEW OF DESIGN

EXCALIBUR is a phase II study.

Excalibur 1 is a three-armed RCT comparing 2nd line systemic chemotherapy to liver transplant and to HAI. Because of the transplant arm, this sub-trial has somewhat stricter inclusion criteria.

Excalibur 2 is a two-armed RCT conducted within the same framework as *Excalibur 1*, but without the transplant arm, and with somewhat wider inclusion criteria (see figure). For analysis, the HAI arm and the systemic chemotherapy arm of *Excalibur 1* and 2 will be directly comparable (stratified for age and primary tumour resected/in situ) and hence boost numbers for this comparison.

[figure not shown]
Study period:

Estimated date of first patient enrolled: February 2021

Anticipated recruitment period: 3 years

Estimated date of last patient completed: November 2024

Treatment duration: up to 2 years

- HAI (intervention group 2) and Systemic therapy (control arm, group 3): Until progression or resection, up to two years
- Transplant (intervention group 1): Until transplant or until removal from list.

Follow-up for outcomes: 10 years

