4.3 Inclusion and exclusion criteria

4.3.1 Inclusion *Excalibur 1 and 2*

Included patients must fulfil the following criteria

1. Primary histology:
 - a. Verified adenocarcinoma in colon/rectum, radically resected with adequate margins/pre-operative treatment
2. Liver metastases:
 - a. Six or more liver metastases that have progression (or insufficient response on 1st line chemotherapy, including toxicity). and are hence planned for 2nd line chemotherapy
3. If a history of confirmed extra hepatic metastatic lesion or local relapse, this must have been successfully treated more than 2 years ago without a new relapse.
4. Chemotherapy
 - a. Planned for 2nd line chemotherapy.
 - b. If patients are switched to 2nd line chemotherapy, randomization can only be allowed prior to first evaluation on 2nd line chemotherapy regimen.
5. The patient
 - a. Good performance status, ECOG 0 or 1.
 - b. Satisfactory blood tests: Hb >10g/dl, neutrophils >1.0 (after any G-CSF), TRC >75, Bilirubin <1.5 x upper normal level, ASAT, ALAT <5 x upper normal level, Creatinine <1.25 x upper normal level. Albumin above lower normal level.
 - c. Women of childbearing potential (WOCBP) must have a confirmed menstrual cycle and a negative highly sensitive pregnancy test prior to inclusion, or two negative pregnancy tests two weeks apart
 - d. WOCBP must agree to use a highly effective method of contraception (see section 6.1.2) for the entire period of exposure to the IMP in the trial, plus for one menstrual cycle/30 days after the last exposure due to the genotoxic potential of the IMP
 - e. Men that may have sexual relations with a WOCBP during the trial must agree to use a condom during intercourse for the entire period of exposure plus for one sperm cycle / 90 days after the last exposure due to the genotoxic potential of the IMP
6. Signed informed consent and expected cooperation of the patients for treatment and follow up must be obtained and documented according to GCP, and national/local regulations.

Exclusion Criteria *Excalibur 1 and 2*

Any of the following criteria will exclude participation in the trial:

1. Arterial anatomy not suited for HAI pump-line insertion.
2. Liver metastatic ingrowth to the diaphragm determined by CT-scan and/or MRI/or ultrasound
3. Previous bone or CNS metastatic disease.

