8 STATISTICAL METHODS AND DATA ANALYSIS

8.1 Determination of Sample Size

We estimate an overall survival at two years in the standard care group (group 3) to be 30 %. We aim to decide whether the use of HAI (group 2) can increase this to 75 % and if liver-TX (group 3) can increase this to 90 %. For a two-sided parallel-group test of proportions to answer both questions with a power of 0.80 and an alpha of 0.05, this will require 16 completed patients per group 3 and 2 to show superiority for HAI over standard care (systemic chemotherapy). An additional 7 patients is needed in the transplant group (1) to show superiority over standard care group (3), bringing the total to 39 patients. This is based on a three-year accrual time, and a total of five-year follow-up from the first patient, ensuring at least two years follow-up for all patients. The trial is not powered to show a difference between group 2 and 1. Adding 15 % to allow for drop-outs, we aim to randomise a total of $18 + 18 + 9 = 45$ patients in a 2:2:1 ratio.

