8.2 Randomization

8.2.1 Allocation-sequence generation

Randomized lists are generated for three groups in *Excalibur 1* in a 1:1:1 distribution and with a variable but unknown block-size of 3 or 6. Further, lists are generated for two groups in *Excalibur 2* in a 1:1 distribution. These will be generated and stored by personell not participating in the trial, and in offices physically removed from the clinical facilities.

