8.2.2 Randomization and allocation procedures

A computer generated random sequence is generated with three groups for *Excalibur 1* and two groups for *Excalibur 2*. Randomization is blocked with a variable and unknown block-size of 2-6. Allocation is by phone to a centralized office physically removed from the clinical premises, or by web and performed after inclusion is judged appropriate and the patient has consented. For patients who are switched to 2nd line chemotherapy, randomization can only be allowed prior to first evaluation on 2nd line chemotherapy regimen.

Patients will be approached, informed and consented by study group members (surgeons or oncologists).

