8.5 Statistical Analysis

8.5.1 Primary analysis

- Primary variable: Overall survival at 2 years from randomization
- Assessment: From the electronic medical records (EPJ)
- Metric: Hazard ratio
- When the last recruited patient has reached two years follow-up or censor.

The primary analysis will be done by Cox regression with treatment group as covariate, adjusted for stratification factors in the randomization.

Primary population: By intention-to-treat (ITT), i.e. all randomized patients regardless of protocol adherence.

The treatment effect will be presented as hazard ratios between the two treatment groups and the standard of care group, in addition to 95% confidence intervals.

The null hypothesis to be tested is that there is no difference between the treatment groups on overall survival after 2 year. If the null hypothesis is rejected on a 5% significance level, the pairwise treatment group's differences will be tested on the 5% level with the family-wise error rate sustained by the closed test principle.

There will be no handling of missing values. All patients will be followed-up until 2 years or death of any reason. Patients lost to follow-up will be censored at time of last observation, and handled accordingly.

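### The primary Cox model does not name Excalibur 1 v 2, the one division the lists use; omitting it biases transplant v pooled controls and costs HAI v control only precision

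*Protocol*

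**What the plan says.** - **Primary model (section 8.5.1):** "The primary analysis will be done by Cox regression with treatment group as covariate, adjusted for stratification factors in the randomization". No factor is named there.
- **Factors named (section 3):** when describing how the HAI and control arms of the two sub-trials will be pooled, the protocol says "stratified for age and primary tumour resected/in situ".
- **Eligibility (section 4.3.1, criterion 1a, both sub-trials):** "Verified adenocarcinoma in colon/rectum, radically resected with adequate margins/pre-operative treatment".
- **Lists (section 8.2.1):** Excalibur 1 is randomised "in a 1:1:1 distribution and with a variable but unknown block-size of 3 or 6", Excalibur 2 "in a 1:1 distribution". No age or primary-tumour strata are mentioned.
- **Blocks (section 8.2.2):** "Randomization is blocked with a variable and unknown block-size of 2-6", without saying which sizes belong to which list.
- **Split (section 8.1):** 18 + 18 + 9 = 45 "patients in a 2:2:1 ratio". The transplant group is to be compared with the whole standard care group. The text gives no number per sub-trial.
- **Excalibur 1-only exclusions:** among others BRAF positivity, age 70 or over, a liver lesion above 10 cm, and stricter limits on extrahepatic disease. Such patients can enter only Excalibur 2.

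**The concern.** The protocol points the primary analysis at a set of factors that its own sections do not agree on. The factors in section 3 are not in the lists, and one of them cannot vary among eligible patients. The split that is in the lists separates patients with different expected survival and is nowhere named as an adjustment factor.

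The stakes differ by comparison. HAI and control are balanced within each sub-trial, so ignoring sub-trial leaves that comparison fair and only less precise. Transplant patients all come from the more strictly selected sub-trial, while about half of the pooled controls come from the other. If Excalibur 2 patients do worse, transplant looks better than it is even with no treatment effect. An analysis plan that copies section 8.5.1 would have no usable factor list to copy.

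**Working it through.** **1. The plan's own sample size.** Two proportions, unpooled variance, two-sided alpha 0.05, power 0.80: n per group = (1.960 + 0.842)² × [p1(1−p1) + p2(1−p2)] / (p1−p2)².
- 30% v 75%: 7.849 × (0.21 + 0.1875) / 0.2025 = 15.4, so 16.
- 30% v 90%: 7.849 × (0.21 + 0.09) / 0.36 = 6.5, so 7.
- 16 + 16 + 7 = 39, and 39 × 1.15 = 44.85, so 45.

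The stated figures reproduce. The sample size itself is not the problem.

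**2. The split.** With n1 of the 45 patients in Excalibur 1, transplant = n1/3 and control = HAI = n1/3 + (45 − n1)/2. Setting n1/3 = 9 gives n1 = 27, and then 9 + 18/2 = 18. So 18:18:9 needs exactly 27 and 18 patients. Otherwise (control:HAI:transplant):
- n1 = 18: 19.5 : 19.5 : 6
- n1 = 36: 16.5 : 16.5 : 12
- n1 = 45: 15 : 15 : 15

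The protocol gives no expected share for Excalibur 1. If each patient falls there independently with an assumed probability, the chance of fewer than 7 transplant patients (n1 of 20 or less) is 78% at 0.4, 28% at 0.5, 2.5% at 0.6 (the share 27/45 that the plan implies) and 0.03% at 0.7.

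**3. HAI v control without and with sub-trial as stratum.** Simulated log-rank (Cox score) test, 18 v 18 with 9 per arm in each sub-trial, exponential survival cut at 2 years. The HAI hazard ratio is ln 0.75 / ln 0.30 = 0.239. Control 2-year survival in Excalibur 1/2 is assumed.

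| Control survival, Exc. 1/2 | Power, unstratified | Power, stratified |
|---|---|---|
| 30/30% | 0.82 | 0.81 |
| 40/20% | 0.80 | 0.81 |
| 50/10% | 0.76 | 0.83 |

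Repeat runs agree to about 0.01.

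**4. Transplant v pooled controls, no treatment effect.** 9 transplant patients (Excalibur 1) against 18 controls (9 per sub-trial), follow-up cut at 2 years, and the control hazard set so that average 2-year survival is 30%. The Excalibur 2 v 1 hazard ratio is assumed. 4,000 runs per row.

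| Hazard ratio, Exc. 2 v 1 | Type I error, unstratified | of which favours transplant | Type I error, stratified |
|---|---|---|---|
| 1 | 5.9% | 2.0% | 5.7% |
| 1.5 | 6.2% | 4.8% | 5.8% |
| 2 | 8.8% | 8.2% | 5.2% |
| 3 | 14.6% | 14.3% | 5.6% |

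A separate simulation gave 6.7%, 9.0% and 14.7% for ratios 1.5, 2 and 3. The baseline lies a little above 5% because the groups are small, so the excess should be judged against about 6%.

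**5. What stratifying costs the transplant comparison.** Restricted to Excalibur 1 controls, 9 v 9 less 15% dropout is 7.65 v 7.65. Power = Φ(0.60 / √[(0.21 + 0.09)/7.65] − 1.960) = 0.86 by the plan's formula. The same formula with pooled controls (7.65 v 15.3) gives 0.96. If only 18 patients enter Excalibur 1 (5.1 v 5.1), the restricted comparison has power 0.70.

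**The case against.** **Section 8.5.1 may already cover sub-trial.** The lists are separate for Excalibur 1 and 2, so a literal reader can count sub-trial as a randomisation factor. Section 3 introduces its factors in the context of analysis, so they may be meant as analysis strata. A separate analysis plan is announced and may settle this. All of that is fair, so the finding is that sub-trial is not named, not that it is excluded. The sections still do not agree.

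**Stronger readings that do not hold.**
- A reader might infer that the empty in-situ level damages the primary estimate. It does not: a constant covariate drops out and the treatment hazard ratio is unchanged. This is an inconsistency between sections 3 and 4.3.1.
- A reader might infer that the two block statements contradict each other, since sizes 2, 4 and 5 cannot balance three arms. Section 8.2.1 gives 3 or 6 for Excalibur 1 only, and the range in 8.2.2 can cover both lists together. It is unclear, not necessarily wrong.
- A reader might infer that small blocks in an open-label, single-centre trial make every second allocation known. That requires a fixed block size known to the recruiter. The protocol says sizes vary and are unknown, and lists are made and kept away from the clinic.
- A reader might infer that the transplant arm will probably be too small. That follows only at low Excalibur 1 shares. At the share the plan implies the risk is 2.5%. The design figure is not shown and may give numbers per sub-trial, and section 8.1 states an aim.

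**The prognostic gap is assumed.** The protocol gives no survival by sub-trial and describes the criteria as only somewhat stricter or wider. That stands, and it is why the effect is shown as a range.

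**Conclusion.** The point holds in this form: sections 3, 4.3.1, 8.2 and 8.5.1 do not yield one list of adjustment factors, and the split that is actually randomised within is not named. Age cannot stand in for it. Patients of 70 or over are confined to Excalibur 2, but so are those with BRAF positivity, large lesions or wider extrahepatic disease.

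For HAI v control the loss is about 1 point of power at assumed control survival of 40/20% and about 7 points at 50/10%, with no bias. For transplant v pooled controls there is bias. Type I error rises from about 6% to about 9% or 15% if the Excalibur 2 v 1 hazard ratio is 2 or 3, nearly all of it in favour of transplant. At 1.5 the two-sided rate barely moves, although the share favouring transplant roughly doubles (2.0% to 4.8%). Stratifying by sub-trial holds the rate at about 5 to 6% throughout.

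The figures rest on exponential survival, 9 patients per arm in each sub-trial, and the assumed gaps. The protocol should be corrected before its wording passes into the analysis plan.

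**What to change.** - **Section 8.5.1:** name sub-trial (Excalibur 1/2) as the stratum of the Cox model for both comparisons, so that transplant is in effect compared with Excalibur 1 controls. State age as a prespecified covariate, not a randomisation stratum.
- **Section 3:** delete the primary-tumour factor, or reconcile it with inclusion criterion 1a.
- **Sections 8.1 and 8.2:** say that 18:18:9 follows from the 1:1:1 and 1:1 lists only with 27 patients in Excalibur 1 and 18 in Excalibur 2. Give these as recruitment targets, or restate the split as approximate. Hard caps would secure it but could close one sub-trial early and turn eligible patients away, so they are a trade-off and not required.
- **Section 8.2:** give the block sizes separately for each list.

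The cost is wording. Stratifying loses slightly if the sub-trials do not differ (0.82 to 0.81 for HAI v control). For transplant it gives up the apparent power from Excalibur 2 controls (0.96 to 0.86 at 9 v 9 randomised), which stays above the planned 0.80 if Excalibur 1 reaches 27.
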